Appendix 3, page 75. CALCULATION of BSA and PASI

Clarification of body surface area calculation and correction in table for calculation of PASI; score of 0 changed from 1% to 0% skin covered with psoriasis and score of 1 changed from 1 - <10% to <10% consistent with published paper (Feldman Feldman SR, Krueger GG. Psoriasis assessment tools in clinical trials. Ann Rheum Dis.2005;64 (suppl II):ii65-ii68.)

	Percentage of skin covered with psoriasis for each of the 4 areas						
Affected	0%	< 10%	10 - < 30%	30 - < 50%	50 - < 70%	70 - < 90%	≥ 90%
Score	0	1	2	3	4	5	6

In addition, the Area Score has been shaded and will be auto-calculated in the eCRF.

Appendix 5. Patient Satisfaction Questionnaire

New appendix added with example questions.

Protocol No. DMVT-505-3003
IQVIA Biotech Study No. GZA92798

**A LONG-TERM, OPEN-LABEL, EXTENSION STUDY TO EVALUATE THE SAFETY
AND EFFICACY OF TAPINAROF CREAM, 1% FOR THE TREATMENT OF PLAQUE
PSORIASIS IN ADULTS**

Statistical Analysis Plan Amendment 2, version 3.0

Document last saved: 16-Nov-2020 8:25 PM

Revision History

Date	Reason for update	Section Updated
21FEB2020	Original Version 1.0	NA
15JUN2020	Amendment 1 Version 2.0	
• Section 11.4 Study Medication and Exposure Compliance
○ Updated the calculation for average grams of study drug administered per doses administered.• Section 11.7 Efficacy endpoint
○ Added PASI-50, PASI-75, PASI-90 analysis• Added Section 11.12 Additional Analyses – COVID-19• Removed Section 11.11.5 Physical Examination• Section 12 Change from the protocol and planned analyses
○ Clarified additional analyses added due to COVID-19
16NOV2020	Amendment 2 Version 3.0	
• Section 8 Handling of missing data
○ Clarified Visit 1 date instead of first dose date will be used in imputation rule of AE dates• Section 10.4 Baseline and change from baseline
○ Updated baseline definition• Section 11.1 Subject disposition
○ Updated definition of number of days in the study• Section 11.4 Study medication exposure and compliance
○ Updated exposure parameter definition• Section 11.7 Efficacy endpoints
○ Updated definition of time to achieving PGA score of 0, duration of treatment episodes, duration of treatment successes• Section 11.11.1 Adverse events
○ Updated treatment-emergent AE definition○ Added a listing for AEs resolved prior to the Visit 1 date○ Added additional TEAE summaries

Table of Contents

Revision History	2
Table of Contents	3
List of Abbreviations and Definitions of Terms	5
1. INTRODUCTION	6
2. STUDY OBJECTIVES	6
3. STUDY DESIGN	6
4. HARDWARE AND SOFTWARE	7
5. DATABASE CLOSURE	7
6. SAMPLE SIZE DETERMINATION	7
7. ANALYSIS POPULATIONS	7
8. HANDLING OF MISSING DATA	8
9. INTERIM ANALYSIS	8
10. DATA CONVENTIONS FOR ANALYSIS	9
10.1 General Statistical Principles	9
10.2 Pooling of Study Sites	9
10.3 Study Day	9
10.4 Baseline and Change from Baseline	9
10.5 Analysis Visit Window	9

1. INTRODUCTION

This Statistical Analysis Plan (SAP), based on the study Protocol Amendment 1 (Version 1.0) dated December 16, 2019, provides additional details concerning the statistical analyses outlined in the protocol and will reflect all changes to the protocol from all amendments. This plan will not repeat all the definitions given in the protocol but will provide further details of the summaries and analyses planned therein.

2. STUDY OBJECTIVES

The objectives of this study are as follows:

- To evaluate the safety and tolerability of tapinarof cream, 1% in adults with plaque psoriasis
- To describe the efficacy of tapinarof cream, 1% over an extended period of time in adults with plaque psoriasis
- To describe the effect of tapinarof cream, 1% on psoriasis symptom severity and the associated impact on daily activities and attitudes in adults with plaque psoriasis

3. STUDY DESIGN

This is a long-term, open-label, multicenter, study to evaluate the safety and efficacy of topical tapinarof cream, 1% in adults with plaque psoriasis. Subjects in this study completed treatment with tapinarof or vehicle in 1 of 2 pivotal Phase 3 efficacy and safety studies (Study DMVT-505-3001 or Study DMVT-505-3002). The study consists of up to 40 weeks of treatment and a 4-week safety follow-up period.

At the completion of the Week-12 Visit of the pivotal study (Visit 1, Baseline [Day 1] in this study), eligibility of the subjects opting to enroll in this extension study is confirmed. Study visits during the treatment period occur every 4 weeks (± 3 days). A Phone Call is performed at Week 2 (Day 15). Unscheduled visits occur, as needed. Subjects who withdraw from the study before Week 40 return to the study center for an Early Termination Visit. The total duration of study participation is approximately 44 weeks.

At the start of the study, subjects entering with a PGA ≥ 1 receive treatment with tapinarof cream, 1% until they achieve a PGA score of 0, at which time treatment is discontinued and subjects are monitored for durability of response. If/when disease worsening occurs, as evidenced by a PGA ≥ 2 , treatment will then be re-initiated and continued until a PGA of 0 is observed.

Subjects entering with a PGA of 0 will have treatment discontinued and they will be monitored for durability of response. If/when disease worsening occurs, as evidenced by a PGA ≥ 2 , treatment is re-initiated and continued until a PGA of 0 is observed.

The pattern of treatment, suspension and re-treatment is continued until the Week 40 visit.

Study drug dispensed to subjects during the clinic visits is applied once daily to all affected areas, including newly appearing lesions and lesions that improve during the study. Subjects

apply sufficient study drug to cover completely each lesion with a thin layer of study drug and record the time of study drug application in a daily diary provided by the study site. Subjects may treat fingernails, toenails, palms, soles, and scalp lesions with study drug; however, improvement of psoriasis is not assessed in these areas.

Safety assessments include AEs, local (application site) tolerability, clinical laboratory tests, vital signs, physical examinations, and investigator-assessed LTS. Efficacy assessments include a 5-point static PGA (0-4 scale), %BSA affected, the PASI, and subject-reported DLQI.

A subject is considered to have completed the study when he/she completes all required procedures/visits for the 40-week (Visit 11) treatment period. The end of the study is defined as when the last active subject has completed the Follow-up Visit.

4. HARDWARE AND SOFTWARE

Statistical analysis will be performed following IQVIA Biotech standard operating procedures and on the IQVIA Biotech computer network. All statistical analysis will be performed using SAS Version 9.4 or greater with program code prepared specifically for the project by qualified IQVIA Biotech statisticians and SAS programmers.

The SAS programs will generate rich-text-formatted (RTF) output with the “RTF” extension using the SAS (ODS). Datasets will be created and taken as input to validated SAS programs to generate the report-ready tables, listings, and figures. Each output display will show the names of the data sets and SAS program used to produce it.

5. DATABASE CLOSURE

After completion of all data review procedures, validation of the project database, and approval of the data review document by the study sponsor, the clinical database will be closed. Any change to the clinical database after this time will require written authorization, with explanation, by the Sponsor and the Biostatistician.

6. SAMPLE SIZE DETERMINATION

The sample size of this study is based on the ICH E1 guideline on extent of population exposure to assess clinical safety for drugs intended for long-term treatment of non-life-threatening conditions. An estimated 850 subjects who complete Study DMVT-505-3001 or Study DMVT-505-3002 will be enrolled in this study at approximately 100 to 120 study sites in the US and Canada. A high discontinuation rate is anticipated in this long-term extension study. Approximately 300 subjects are expected to complete the study (40 weeks of treatment).

7. ANALYSIS POPULATIONS

Intent-To-Treat (ITT) Analysis Set: includes all subjects enrolled into the study. All subjects who signed the informed consent will have enrolled in the study. All efficacy and safety analysis will be performed over ITT analysis set.

Subjects will be analyzed overall and by the original treatment assigned in pivotal studies (DMVT-505-3001 and DMVT-505-3002). This will be referred to below as DB (double-blind) treatment group.

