4.5. Screening Failure

Screen failures are defined as subjects who consent to participate in the clinical study but are not subsequently enrolled. A minimal set of screen failure information is required to ensure transpivotal reporting of screen failure subjects to meet the Consolidated Standards of Reporting Trials publishing requirements and to respond to queries from regulatory authorities. Minimal information includes demography, screen failure details, eligibility criteria, and any SAEs. These data will also be linked to subject data from the initial study.

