7.1. Visit 1; Baseline

On Day 1, subjects from the pivotal studies who were considered eligible for this study will sign the ICF and be reassessed to confirm eligibility to participate in this study. All subjects who continue to meet study eligibility criteria will be enrolled. Subjects entering with a PGA ≥ 1 will receive treatment with tapinarof cream, 1% until they achieve a PGA score of 0, at which time treatment will be discontinued and subjects monitored for durability of response. If/when disease worsening occurs, as evidenced by a PGA ≥ 2 , treatment will then be re-initiated and continued until a PGA of 0 is observed. Subjects entering with a PGA of 0 will have treatment discontinued and be monitored for durability of response

The following procedures and assessments will be performed at the Baseline Visit:

- Brief physical exam (last assessment from pivotal study)
- Vital signs measurements (last assessment from pivotal study)
- Urine pregnancy test (females of CBP; last assessment from pivotal study)
- Blood sample collection for clinical laboratory tests (serum chemistry, hematology, diagnostic tests; last assessment from pivotal study)
- Urinalysis
- Photography of a representative area of the subject’s disease area (optional for subjects; at a subset of study centers) (last assessment from pivotal study)
- PGA score (last assessment from pivotal study)
- BSA affected calculation (last assessment from pivotal study)
- PASI (last assessment from pivotal study)
- DLQI (last assessment from pivotal study)
- AE recording (Including any ongoing AEs from the pivotal study and from the time the ICF is signed)
- Concomitant medication recording (from the time ICF is signed)
- Diary dispensed (subjects will be instructed in how and when to complete diary), if applicable
- Dispense study drug, if applicable

- Instruction on how to apply study drug, if applicable
- Study drug application under supervision, if applicable

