10.3. Analysis Populations

All subjects enrolled into the study will be included in the intent-to-treat (ITT) analysis set.

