10.4. Planned Analyses

All efficacy and safety measures over the course of the study will be presented. All analyses will be based on the ITT population. Details of planned analyses will be described in the Statistical Analysis Plan (SAP), which will be finalized prior to database lock.

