11.11 Safety Analysis

All safety parameters will be summarized over the ITT population of all enrolled subjects, overall and by DB treatment group.

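### SAP section 7 equates consent with enrolment against the protocol, and AE and AESI incidence has no summary restricted to subjects who applied drug in this study

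*SAP*

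**What the plan says.** **Who is in the ITT set.** Protocol 10.3 defines it by enrolment: "All subjects enrolled into the study will be included in the intent-to-treat (ITT) analysis set". SAP section 7 begins the same way, then adds "All subjects who signed the informed consent will have enrolled in the study".

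**How the protocol treats consent.** Section 4.5 says "Screen failures are defined as subjects who consent to participate in the clinical study but are not subsequently enrolled". Section 7.1 sets the order at Visit 1 as signature, reassessment, enrolment: "All subjects who continue to meet study eligibility criteria will be enrolled". SAP section 12, which lists departures from the protocol, does not mention a consent rule.

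**Which set is used for safety.** Protocol 10.4 says "All analyses will be based on the ITT population". SAP section 7 says "All efficacy and safety analysis will be performed over ITT analysis set", and SAP 11.11 repeats it: "All safety parameters will be summarized over the ITT population of all enrolled subjects, overall and by DB treatment group". Neither document defines a set of dosed subjects. SAP 11.1 does count subjects who used any study drug, but only for disposition.

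**Who may go undosed.** Under protocol 3.1 and 5.1.5.3, a subject entering at PGA 0 gets no drug unless PGA reaches 2 or more. Protocol 3.1 also says that entrants come from either the tapinarof or the vehicle arm of the pivotal studies.

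**The concern.** There are two separate problems.

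The first is a conflict of definition. The protocol allows a subject to consent without being enrolled; the SAP sentence does not. Because it sits inside the population definition, a programmer could derive the ITT flag from the consent date and bring in people the protocol calls screen failures.

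The second is the denominator. The sample size rests on the ICH E1 guideline on extent of exposure, so the natural safety question is how often events occur in people using the drug. With all enrolled subjects as the only population, AE and AESI incidence mixes them with people who applied none here. A PGA-0 entrant from the vehicle arm who never worsens would have had no tapinarof in either study.

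**Working it through.** **1. The plan's own figures.** The 850 planned and roughly 300 expected completers (SAP section 6) are exposure-based estimates. With no event rate, precision target or discontinuation rate given, 850 cannot be reproduced independently. The two counts imply discontinuation of 1 − 300/850 = 64.7%.

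**2. The two enrolment rules side by side.**

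| Step | Protocol 4.5, 7.1, 10.3 | SAP section 7 |
|---|---|---|
| Signs consent | Not yet enrolled | Enrolled |
| Fails recheck | Screen failure, outside ITT | Inside ITT if the sentence is a definition |
| Passes recheck | Enrolled, in ITT | In ITT |

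The rules differ only for a subject who consents and then fails. No count of such subjects is given. The 850 is planned enrolment, so under the protocol any screen failures would be additional to it.

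**3. How never-dosed subjects reach the denominator.** They are validly enrolled, so protocol 10.3 places them in ITT and 10.4 bases every analysis on ITT. Correcting the consent sentence would not remove one of them. The group is foreseen: SAP 11.7 plans the proportion of PGA-0 entrants who never reach PGA ≥2. With 64.7% discontinuation implied, others may leave before a first worsening.

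**4. Size of the dilution.** Inputs:
- p = true incidence in dosed subjects (5% and 20%, illustrative)
- f = share of the ITT set never dosed in this study (assumed 1% to 10%; not in the documents)
- r = AE rate in never-dosed subjects divided by that in dosed subjects (assumed 0, 0.5 or 1)

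Reported incidence = p × [(1 − f) + r × f].

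| p | f | r = 0 | r = 0.5 | r = 1 |
|---|---|---|---|---|
| 20% | 1% | 19.8% | 19.9% | 20.0% |
| 20% | 5% | 19.0% | 19.5% | 20.0% |
| 20% | 10% | 18.0% | 19.0% | 20.0% |
| 5% | 1% | 4.95% | 4.975% | 5.0% |
| 5% | 5% | 4.75% | 4.875% | 5.0% |
| 5% | 10% | 4.5% | 4.75% | 5.0% |

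For example, with p = 20%, f = 10% and r = 0: 0.20 × 0.90 = 18.0%.

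For an event never seen, the one-sided 95% upper bound is 1 − 0.05^(1/n). With n = 850 it is 0.352%; with the 765 dosed at f = 10% (850 × 0.90), it is 0.391%.

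**5. Which r applies depends on an unresolved conflict.** Protocol 10.4.3 restricts AE summaries to events after the first dose of study drug. If that means the first dose in this study, a never-dosed subject can never enter the numerator, so r = 0 by construction. SAP 11.11.1 counts as treatment-emergent every AE reported in this study, except those carried over from the pivotal study that resolved before Visit 1. No dose is required, so r can be above 0. Under SAP section 8, an AE with missing causality in such a subject would be counted as related to study drug.

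**6. Which summaries are touched.** AE and AESI incidence. The Local Tolerability Scale (LTS) is required only when the subject was applying drug before the visit (protocol Table 1 footnote i, and 6.3.5), so never-dosed subjects should contribute no scores. By-visit laboratory and vital-sign summaries rest on subjects with data.

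**The case against.** **The consent sentence may be harmless.** It can be read as an expectation that nobody will fail, since section 7 first defines ITT by enrolment. Subjects already considered eligible are rechecked at a visit that coincides with pivotal Week 12, so failures are probably few, perhaps none. That limits the effect, but the sentence still conflicts with protocol 4.5 and sits where it can be programmed.

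**The SAP follows the protocol.** Basing safety on ITT is the protocol's choice. A dosed-subject table is therefore an added analysis, not the correction of a SAP error. This stands.

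**Off-drug time is part of the design.** The study evaluates intermittent use with monitoring after clearance. PGA-0 entrants from the tapinarof arm have just finished 12 weeks of treatment, and a dosed-only set would lose their events. This also stands, and is the reason to keep the ITT tables.

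**Readers can see the undosed count.** SAP 11.1 and 11.4 report drug use and exposure. That shows how many were undosed, but not incidence among the dosed. The general allowance in SAP 10.1 for denominators that suit the purpose does not clearly override the specific rule in 11.11.

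**Stronger readings not supported.** A reader might infer that the consent sentence brings in the never-dosed subjects, or that every safety denominator, including LTS, is diluted; steps 3 and 6 show otherwise. A reader might also infer that dilution distorts the comparison of the original double-blind (DB) groups. That is plausible, because tapinarof outperformed vehicle in Phase 2b and PGA-0 entry may be commoner in its former arm. But the documents give no PGA-0 counts by group, and no testing is planned.

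**Conclusion.** The point holds in two limited parts. The consent sentence conflicts with protocol 4.5 and 7.1; its numerical effect depends on an unstated number of screen failures and is probably small. Separately, AE and AESI incidence is planned only over all enrolled subjects, including PGA-0 entrants who never restart treatment.

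Over an assumed never-dosed share of 1% to 10%, and with no events in those subjects, a true 20% becomes 19.8% to 18.0%. That is the largest understatement for a given share. A reader might infer a fixed understatement, but the documents give neither the share nor the AE rate in these subjects, and the dilution vanishes if the rates are equal. The effect is modest, but incidence among exposed subjects is worth reporting in a study sized on exposure.

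**What to change.** 1. Replace the consent sentence in SAP section 7 so that ITT means subjects who consented, were confirmed eligible and were enrolled at Visit 1, matching protocol 4.5, 7.1 and 10.3.
2. Add AE and AESI incidence tables, overall and by DB group, for subjects with at least one application in this study. Use the flag already needed for SAP 11.1. Keep the ITT tables, show AEs in never-dosed subjects separately, and record the addition in SAP section 12.
3. Reconcile the treatment-emergent definition in SAP 11.11.1 with the after-first-dose window in protocol 10.4.3, saying whether first dose means first in this study and how events before a PGA-0 entrant's first application are handled.

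The cost is a few sentences and a few extra tables. In the dosed-subject tables, stated incidences may be slightly higher. Those tables omit off-drug events in never-restarted PGA-0 subjects from the tapinarof arm, so they should accompany the ITT tables, not replace them.

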8. HANDLING OF MISSING DATA

Efficacy endpoints will be summarized by visit using observed cases (OC) and last observation carried forward (LOCF) methods as appropriate. Baseline values will not be carried forward.

Imputation of Start and End Dates of Adverse Event (AE)

To calculate duration of Adverse Events, the following rules will be used where applicable to impute partial or completely missing start dates or end dates:

- If only the day is missing for a start date, the 1st of the month will be imputed. If the new estimated date falls before the Visit 1 date, while the known month and year match the month and year of the Visit 1 date, the date of Visit 1 will be used as the new estimated date.
- If only the day is missing for an end date, the last day of the month will be imputed. If the new estimated date falls after the date of last study visit, the date of last study visit will be used as the new estimated date.
- If both the day and the month are missing for a start date or end date, no imputation will be used, and the duration will not be calculated.
- If the start date or end date is completely missing, duration will not be calculated.

For AEs ongoing at the end of pivotal studies, duration will be computed using the DMVT-505-3003 visit 1 date as the AE start date.

If relationship of AE to treatment is missing, the event will be conservatively considered as being related to study drug. Missing AE severity will be imputed to the highest severity level (most severe). Through the data cleaning process, all attempts will be made to avoid missing values for relationship and severity.

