6.3. Safety Assessments

6.3.1. Adverse Events

All AEs will be collected from the time the subject signs the ICF until the final visit/contact with the subject. Adverse events that began during the pivotal study and were ongoing at the end of that study will be reported as ongoing AEs. Additional safety information, including the definition of an AE and the methods for recording, evaluating, and assessing causality of AEs and the procedures for completing and transmitting SAE reports are provided in Section 8.

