8.3.2. Follow-up of Adverse Events

After the initial AE/SAE report, the Investigator is required to proactively follow each Subject at subsequent visits/contacts. All SAEs and nonserious AEs will be followed until resolution, until the condition stabilizes, until the event is otherwise explained, or until the subject is lost to follow-up.

The Investigator will assess the outcome of each AE using the following criteria:

- **Recovered/Resolved:** The event has improved or subject recuperated.
- **Recovered/Resolved with sequelae:** The subject has recuperated but retained pathological conditions resulting from the prior disease or injury.
- **Recovering/Resolving:** The event is improving.
- **Not recovered/Not resolved:** The event has not improved or subject recuperated.
- **Unknown:** The outcome of the event is not known, not observed, not recorded, or refused
- **Fatal:** Termination of life as an outcome of the AE.

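### SAP 8 sets a day-missing AE end date back to the last study visit even when the recorded end month is later, which understates that event's duration

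*SAP*

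**What the plan says.** SAP 8 introduces its date rules as follows: "To calculate duration of Adverse Events, the following rules will be used where applicable to impute partial or completely missing start dates or end dates". For an end date with a known month and year, "If only the day is missing for an end date, the last day of the month will be imputed". It continues: "If the new estimated date falls after the date of last study visit, the date of last study visit will be used". The sentence sets no condition on the recorded month and makes no comparison with the event's start date.

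The bullet above it handles start dates differently. An imputed start that falls before Visit 1 is moved to Visit 1 only "while the known month and year match the month and year of the Visit 1 date".

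Protocol 8.3.2 puts no calendar limit on follow-up: "All SAEs and nonserious AEs will be followed until resolution, until the condition stabilizes".

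SAP 11.11.1 uses duration in two places: the by-subject TEAE listing, and the AESI summary (contact dermatitis, folliculitis, headache), which takes each subject's maximum duration. The AESI duration summary leaves out AESIs still ongoing at end of study. The SAP does not say how that status is decided for an AESI later recorded as resolved.

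**The concern.** An imputed date should fill in what is missing without contradicting what was recorded. If the site recorded the month of resolution and that month comes after the month of the last visit, the last-visit date cannot be the end date. The cap imposes it anyway, and the error always shortens the event.

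The rule also treats like events differently. Two events with the same start and the same true end after the last visit get different durations if one has a complete end date and the other lacks the day. A deliberate convention of truncating at the end of participation would cap both.

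The direction is at odds with the rest of SAP 8, which sends missing severity to the highest level and missing relationship to related. What is at stake is the accuracy of reported AE durations in a study whose first objective is safety and tolerability.

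**Working it through.** The documents give no figure to reproduce, so the check applies the rule as written to test dates. Neither document gives a formula for AE duration. I assume duration = end − start + 1; without the +1, every duration below falls by one day and the differences do not change. All dates are illustrative.

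**1. Onset before the last visit, end month after it**

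Start 10 October, last visit 20 October, recorded end December with day unknown.

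- Imputed end before the cap: 31 December. This is after 20 October, so the cap sets it to 20 October.
- Duration under the rule: 20 Oct − 10 Oct + 1 = 11 days.
- Shortest duration the record allows (1 December): 52 + 1 = 53 days.
- Longest (31 December): 82 + 1 = 83 days.
- Understatement: 53 − 11 = 42 to 83 − 11 = 72 days.

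Had a complete December date been recorded, no rule in SAP 8 would have changed it.

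**2. End month equal to the last-visit month**

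Take Visit 1 as 10 January 2020 and the last visit as Day 309, 13 November 2020. With onset 1 November and recorded end November 2020, the cap gives 13 November. That date is possible, so here the cap does not contradict the record. With the end recorded as December 2020, 13 November is at least 18 days too early; as January 2021, at least 49 days.

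**3. Onset after the last visit (edge case)**

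Last attended visit 10 August, start 25 August, recorded end September with day unknown. Duration under the rule is 10 Aug − 25 Aug + 1 = −14 days. The record allows 8 (1 September) to 37 (30 September).

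**4. How far the edge case extends**

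On the 2020 dates of step 2, I ran a grid of true end dates 0 to 119 days after onset, with the end day treated as missing:

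| Onset | Combinations | End before start, rule as written | With month/year condition added |
|---|---|---|---|
| On or before last visit | 309 × 120 = 37,080 | 0 | not tabulated |
| After last visit | 31 × 120 = 3,720 | 3,720 | 153 |

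The remaining 153 have onset from 14 to 30 November and an end in the same month (1 + 2 + … + 17 = 153). The month condition leaves the cap in force there, so a second condition tied to the start date is needed. These are counts of date combinations, not event rates.

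**5. Whether onset after the last visit can be recorded**

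Protocol 6.3.1 allows it: "All AEs will be collected from the time the subject signs the ICF until the final visit/contact with the subject". Protocol 8.2.2 extends collection of related events to any follow-up contact, and the TEAE definition in SAP 11.11.1 has no upper limit on onset. Protocol 8.3.1 (general collection) and 10.4.3 (summary window), read alone, stop at the final visit.

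**The case against.** The strongest objection is that the one summary using duration may already exclude these events. An AESI whose end month is after the last visit was, on a natural reading, still ongoing when the subject's study ended, and SAP 11.11.1 then drops it. On that reading the cap changes nothing in the AESI duration summary. This stands as a limit. A reader might infer that the rule makes persistent AESIs look brief; the documents support that only if an AESI later recorded as resolved is not counted as ongoing at end of study. The TEAE listing carries the wrong duration either way.

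A reader might also infer that negative durations are a general result. They are not. They require onset after the last study visit, a later contact that is not itself a visit, and a missing end day. Protocol 4.6.3 asks for every effort to hold an Early Termination Visit, the only scheduled phone contact is at Week 2 (Protocol 7.5), and SAP 11.12 counts phone and virtual visits as altered study visits.

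A third tempting inference is that affected events are the long ones, concentrated among the roughly 550 expected non-completers (850 − 300). The documents show neither. A brief event that starts just before the last visit can outlast it, and completers' events can also outlast their last visit.

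Finally, incidence, severity, relatedness, seriousness and AESI time to first event do not use the end date, and nothing is tested (SAP 10.1). All of that is correct. It limits the importance of the defect but does not make the imputed date right.

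**Conclusion.** The rule is wrong as written, at low severity: a correction worth making but not a threat to the study's conclusions. For an end date with the day missing and a recorded month later than that of the last visit, SAP 8 imputes a date that the record excludes and so understates duration. In the worked example the shortfall is 42 to 72 days; in general it depends on how far the recorded month lies beyond the last visit.

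The consequence is confined to descriptive duration in the TEAE listing and, subject to the reading of ongoing at end of study, the AESI duration summary. An imputed end before the start is possible only for onset after the last visit, on which the protocol's own sections differ. The conclusion does not depend on that case or on the assumed duration formula. How many events are affected is unknown, because the documents give no rate of partial dates.

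**What to change.** In SAP 8:

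- Apply the cap only when the known month and year of the end date match those of the last study visit. Otherwise keep the last day of the known month.
- Do not let an imputed end date precede the event's start date.

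In SAP 11.11.1, state whether an AESI with an end date after the last visit counts as ongoing at end of study for the duration summary.

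In the October example the imputed end becomes 31 December and the duration 83 days, the top of the range the record allows and in keeping with the last-day-of-month rule. In the grid, the month condition reduces the end-before-start cases from 3,720 to 153, and the start-date condition removes the rest.

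The cost is a few words in two SAP sections and a small change to the date-imputation program. No new data are needed.
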